Compression Hosiery to avoid the Post Thrombotic Syndrome (CHAPS)

Statistical Analysis Plan

Version No	
Date Finalised	
Author(s)	[name] and [name]
CI Name	[name] [name]
CI Email address	[contact]

Signatures		
Trial Statistician:	Date: 04/05/2023	
[name]		
^		
Chief Investigator:	Date: 03/05/2023	
Cinci investigatori		
[name]		

Document Control				
Version No	Date	Summary of Revisions		
1.0		Initial Creation		
2.0	03-05-2023			

Table of Contents

List	List of Abbreviations2		
1.	Introduction	4	
ОВ	BJECTIVES and OUTCOMES	5	
F	Primary Objective	5	
9	Secondary Objectives	5	
F	Primary Endpoint	5	
9	Secondary Endpoints	6	
2.	Statistical Methods section from the protocol	9	
3.	Overall Statistical Principles	11	
Un	nivariable analysis	11	
Μu	ultiplicity	12	
4.	List of Analyses	12	
5.	Validation and QC	15	
6.	References	16	

Abbreviation	Full name	
DVT	Deep Venous Thrombosis	
PTS	Post-thrombotic Syndrome	
ICER	Incremental cost-effectiveness ratio	
ABPI	Ankle brachial pressure index	
CI	Chief Investigator	
CACE	Complier average causal estimation	
IQR	Interquartile range	
SD	Standard deviation	
MAR	Missing at random	
MCAR	Missing completely at random	

Changes to the Statistical Analysis Plan

The CHAPS study was terminated early on 20th May 2022 by the funder NIHR/HTA withdrawing funds on the basis of poor recruitment in the context of the NHS and the COVID-19 pandemic. The last patient last visit was 31 Dec 2022. At closure the study had recruited around 152 of the 864 target sample size. The original sample size calculation required 864 to have 90% power at a 5% level of significance to detect an absolute reduction in the incidence of PTS from 30% in the standard of care arm to 20% in the stockings plus standard of care arm, allowing for 10% loss to follow up. With just n=152 randomised, and 10% lost to follow up, the study would be powered at 90% to detect a reduction from 30% to 9%, or a 70% relative reduction (21% absolute reduction) which was considered clinically implausible.

The Statistical Analysis Plan was then changed throughout to remove any formal statistical comparisons, making the analysis purely descriptive.

1. Introduction

Deep venous thrombosis (DVT) occurs in approximately 1-2 per 1000 adults in the UK (1) and just under half will go on to develop lifelong disability from post-thrombotic syndrome (PTS) (2). PTS is defined as "chronic venous symptoms or signs secondary to deep vein thrombosis" e.g. lifelong leg pain, oedema and skin changes, progressing in 5% to venous ulceration (3). The pathophysiology of post- thrombotic syndrome is sustained venous hypertension from venous outflow obstruction and valvular incompetence (4). Three clinical scales are widely used to diagnose PTS after objectively-diagnosed DVT, Brandjes scale (5), Ginsberg measure (6) and Villalta scale (7) with the Villalta considered the "gold standard" for the diagnosis and classification of post-thrombotic syndrome (8).

The average age of patients developing PTS is 55 years (9), meaning that around half of patients work to support a family. Of patients having a lower limb DVT, around 30% of patients will develop mild PTS, 10% moderate and 5% severe PTS (2, 9). Severe PTS is characterised by leg ulceration. The incidence of DVT rises markedly with age (10) and the

Date Finalised

severity of PTS increases with age and body mass index (2) . With an older, heavier UK

population in the future, the burden of PTS is set to rise.

OBJECTIVES and OUTCOMES

Primary Objective

To measure the difference in incidence of post-thrombotic syndrome at a median of 18

months follow up after first, acute DVT between standard clinical care (anticoagulation) and

the intervention arm (a graduated compression stocking and the standard clinical care

(anticoagulation)). With the study terminated early, the follow up was determined by what

was available at database lock, with no expectation anymore that the median would be 18

months as originally specified. The last patient last visit occurred on 31 Dec 2022.

Secondary Objectives

To compare specific and generic quality of life at the end of the trial

To compare employment status at the end of the trial

To evaluate whether the use of stockings to prevent PTS is cost effective

• To perform a detailed process evaluation to understand barriers to adherence

To measure adherence in detail over the initial first year and at the end of the trial

To capture off-label stocking use in the standard care arm

Primary Endpoint

The primary outcome measure is any incidence of PTS using the validated Villalta's score. The

original intention was with a 2 year recruitment period with a constant rate of recruitment

the follow up would have a median of 18 months (with a range 6 to 30 months), and that the

primary outcome will be recorded at fixed time points for all those randomised; at 6 and 12

months post randomisation and at study end (estimated to be a median of 18 months, range

6-30 months). However, with the early closure and the non-constant, lower than anticipated recruitment rate, with interruptions for the COVID-19 pandemic, the anticipated median, range, and scheduled times for measuring PTS were not adhered to. The descriptive analysis will now instead summarise all data that was captured, with no formal statistical analysis.

Secondary Endpoints

- Venous ulceration incidence as measured by the validated Villalta's score
- Employment status-(change in number of days working from baseline)
- Change in disease-specific and generic quality of life- VEINES-QoL and EuroQoL EQ5D scales from baseline over 6m, 12m and end of study visit

Secondary endpoints removed due to funder terminating study early

- Adherence to stockings and anticoagulants- patient self-report
- Cost-effectiveness of stocking prescription- Incremental cost-effectiveness ratio
 (ICER) from the EQ-5D questionnaire, with appropriate sensitivity analysis

Study Design

CHAPS is a UK, multi-centre, pragmatic, blinded outcome assessment, randomised controlled trial. The original 45-month trial was intended to follow up patients with first, acute lower limb DVT for a median of 18 months (range 6 – 30 months) and be conducted in approximately 11 secondary care Trusts in the United Kingdom.

[figure not shown]
The original sample size was n=864 randomised 1:1 to standard care (anticoagulation as per local hospital guidelines) or intervention (anticoagulation as per local hospital guidelines and regular use of a graduated compression stocking).

CHAPS had an internal pilot study which was designed to the first 200 patients (100 intervention, 100 control) for one year and provide detailed information on stocking use in both arms. At six months median follow up, the criteria for continuing CHAPS would have been \geq 70% of participants wearing stockings (self-reported patient adherence) for \geq 4 days per week in the intervention arm, along with a documented reorder of stockings within the last 6 months.

A parallel process evaluation was included to complement the main CHAPS trial with the aim to better understand how and why the educational elements of the intervention were effective or ineffective. This would have identified contextually relevant strategies for successful implementation through detailed descriptions of the participants' views and experiences of wearing graduated compression stockings and assessed patients' perspectives of the stockings by applying a mixed-methods approach to identify the salient perceptions and practicalities influencing patients' motivation and ability to use the stockings as recommended.

The study was terminated before the 200 patient threshold was achieved and the sub study on adherence and the process evaluation were abandoned, along with the health economic evaluation.

Figure 1. Study Flowchart

ELIGIBILITY CRITERIA

Inclusion Criteria

- Symptomatic presentation of first deep vein thrombosis, <2 weeks from diagnosis
- Imaging confirmed, lower limb deep vein thrombosis (popliteal, femoral, iliac or combination)
- Ability to give informed consent
- Age 18 or over

Exclusion Criteria

- Life expectancy < 2 years
- Contraindication to wearing graduated compression stockings
- Previously intolerant of or already wearing graduated compression stockings for more than 1 month.
- Ankle brachial pressure index (ABPI) < 0.8 or pedal pulses absent
- Bilateral deep vein thrombosis
- Previous chronic venous insufficiency (patients with existing chronic skin changes or ulceration, defined as C4,5,6 by CEAP classification)
- Pre-existing post thrombotic syndrome, significant leg pain (e.g. knee arthritis, spinal claudication) or oedema (e.g. lymphoedema).
- Newly diagnosed cancer, metastatic cancer, or cancer undergoing active treatment or palliation
- Contraindication to anticoagulation
- Known allergy to fabric in compression stockings

2. Statistical Methods section from the protocol

Quantitative analysis and oversight will be performed in conjunction with the Edinburgh Clinical Trials Unit (ECTU). ECTU will work closely with the CI and trial manager on the delivery of the data management and statistical aspects of the study, in compliance with the applicable

Statistical Analysis Plan <<CHAPS>> Version No 1.0

Date Finalised

regulations. These analyses will now be purely descriptive given the early termination of the

study.

(i) Primary Endpoint Analysis

The intention was that at a median of 18 months (range 6-30 months) patients will be seen

by an independent, blinded observer to assess their degree of post-thrombotic syndrome

using the validated semi-quantitative Villalta scoring system. The median of 18 months is no

longer achievable given the slow recruitment, impact of the pandemic, and early closure of

the study at 152 participants.

The primary analysis will be an intention-to-treat analysis that does not adjust for adherence

to stockings. This will tell us the treatment effect given the observed adherence, which is

appropriate to gauge real-world performance.

We will use a time-to-first-event approach since it is possible that the treatment effect may

be a combination of averting PTS, but also in those that develop PTS the onset may be

delayed. These analyses will be purely descriptive. Confidence intervals will be reported, but

no P-values for statistical tests of hypothesis.

(ii) Secondary Endpoints Analysis

Secondary analysis will determine how much the behavioural components affect adherence;

firstly, whether behavioural components change participants knowledge, beliefs and

intentions regarding stocking usage. These analyses will be purely descriptive. Confidence

intervals will be reported, but no P-values for statistical tests of hypothesis.

The original intention was to determine what extent compliance has indeed mediated

outcome using Complier Average Causal Estimation (CACE) causal modelling through

instrumental variable regression i.e. does better compliance improve outcomes; and looking

ahead, whether future development of behavioural components is likely to be beneficial.

Statistical Analysis Plan << CHAPS>>

Version No 1.0
Date Finalised

These causal models will not be undertaken, given the achieved sample size of 152 before

early termination.

3. Overall Statistical Principles

Descriptive analysis will be conducted to present the variables (base line demographic data,

working status, baseline vital signs, baseline lifestyle information, Villalta scores, past medical

history) split by the two study arms (medicine and stocking or only medicine). We will present

dichotomous and categorical variables as counts (percentages) in each category.

Furthermore, we will present continuous variables as mean, standard deviation (SD), median,

interquartile range (IQR), minimum and maximum.

Originally, all performed statistical tests would have been two-sided with a significance level

of 5%. Given the early termination of the study, no formal statistical tests will now be

performed.

Two-sided 95% confidence interval will be presented.

Proportion of missing data will be recorded for all variables. The original intention of

conducting sensitivity analyses to explore the robustness of the reported findings to observed

patterns of missing data have been abandoned due to the early termination leading to a final

sample size of 152.

Univariable analysis

The normality of the continuous variables was to be examined visually by constructing

histograms and Q-Q plot. The difference between the two study arms was to be examined

using a t-test for continuous variables that are normally distributed and Mann-Whitney U-test

if the normality assumption is violated. Furthermore, Chi-square test will be employed to

examine the difference between the two study groups for dichotomous and categorical

variables.

Page **11** of **17**

Statistical Analysis Plan <<CHAPS>> Version No 1.0

Date Finalised

Due to the early termination of the study, these between randomised groups comparisons

will be calculated descriptively and 95% confidence intervals reported, but now no formal

statistical test of hypothesis will be undertaken, and no P-values reported.

Multiplicity

There was to be no adjustment for multiplicity in any of the conducted analyses because they

address the pre-specified objectives and there is only one primary outcome. Secondary

outcomes are for explanatory purposes and they are pre-specified. Furthermore, the number

of performed analyses will be clearly recorded in any publications resulting from this trial.

This is no longer relevant as no formal statistical tests of hypothesis are being undertaken.

4. List of Analyses

Primary outcome (Binary)

Multivariable analysis

Given the limited sample size, no multivariable model to adjust the treatment effect for

known strongly prognostic baseline factors will now be fitted.

We had intended to construct a multivariable logistic regression model. Categorical variables

will be analysed using chi-square. Continuous variables that are normally distributed will be

analysed using t-test while those that are not meet the normality assumption will be analysed

using Mann-Whitney U-test. Covariates with a P-value < 0.2 will be considered for inclusion

in the final model (11). The likelihood ratio test will be employed to select the variables for

the best model fit. Furthermore, to allow for clustering on care trusts, we will use mixed effect

logistic regression model by including the care trusts as a random effect. Furthermore, we will

consider performing a Poisson or negative binomial regression (if the assumptions of the

Poisson regression do not hold) with including the duration of follow up as an offset variable.

None of this multivariable modelling will now be considered.

Binary secondary outcomes

A generalised linear mixed model with a logit link function will be constructed. Care trusts will be included as a random effect in the final model. We will present the results in odds ratio (OR) with the corresponding 95% CI and P-value. Again, given the early termination of the study, none of this modelling will be undertaken.

Continuous secondary outcome

Again, due to the small sample size given the early termination of the study, this proposed modelling will now not take place. A normal linear mixed model would have been constructed to analyse these outcomes. Care trusts will be included as a random effect in the final model. The adjusted mean difference with the corresponding 95% CI and P-value will be reported. The normality assumption will be tested using the normal probability plot. If the normality assumption does not hold, the outcome will be transform. In the event that the normality assumption is not met after transforming the outcome, alternative methods including categorising the outcome will be considered. We will adopt the same method if the residual versus fitted values show non-constant variance for the outcome.

Score derivation

The questionnaires used to produce the scores employed in this study are included in the case report forms (CRFs). The scores are derived as follows

Villalta's Score

Villalta's score is a disease specific clinical measure that can be used to both diagnose and categorise the severity of PTS (12). (Five patient-rated symptoms (pain, cramps, heaviness, pins and needles, itching) and six physical signs (pretibial edema, skin induration, hyperpigmentation, pain during calf compression, venous ectasia, redness) are graded for intensity (0 points=absent, 1 point=mild, 2 points=moderate, 3 points=severe). The points are summed into a total score. The range of scores for symptoms is 0-15, for signs is 0-18, and for total score is 0-33. The presence of a venous leg ulcer is also documented and classified as

Statistical Analysis Plan <<CHAPS>> Version No 1.0

Date Finalised

severe regardless of the presence or absence of other signs or symptoms. The patient is

diagnosed as having PTS if the Vilallta score is ≥5 or if a venous ulcer was present. A score of

5-9 signifies mild disease, 10-14 moderate disease, and ≥15 severe disease. The Villalta's scale

can be administered at any time during follow up if there is clinical suspicion of PTS or the

patient reports symptoms outside the face to face follow up visits.

VEINES-QOL

The VEINES-QOL questionnaire is a disease-specific quality of life tool for the venous disorder

of the leg (CVDL) (13). It covers 26 items; ten questions about manifestations due to CVDL,

nine items about constraints in daily activities due to CVDL and five items on psychological

influence (14). Besides, it contains one item on the difference in the patient's leg problem

over one year and one item on the time of day that the leg problem is most intense (14). The

derivation of the VEINES-QOL scores and dealing with missing elements in the questionnaire

will be based on the method published by Bland et al (13).

EQ-5D-5L

The EQ-5D-5L health scale and EQ-5D-5L health index will be included in the analysis. EQ-5D-

5L health scale is based on the EuroQOL group 5-dimension 5-level questionnaire health scale

which is a visual analogue ranging from 0 to 100 (the higher the score, the better the health

is) (15). Furthermore, the EQ-5D-5L health index is calculated using the value set for England

(16). It ranges from 0 to 1 with the higher score showing better health (15).

5. Validation and QC

A second statistician will do the following to validate the main statistician's work

- 1. Performing the analysis and checking the results and conclusions of the primary analysis.

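### The change-from-baseline secondary endpoints get no baseline-adjusted estimate, so their 95% CIs are valid but wider than the collected data allow, and small sample size does not justify this

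*SAP*

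**What the plan says.** - Under Secondary Endpoints, quality of life is "Change in disease-specific and generic quality of life- VEINES-QoL and EuroQoL EQ5D scales from baseline over 6m, 12m and end of study visit", and employment is "Employment status-(change in number of days working from baseline". Both are change-from-baseline endpoints and both survive early termination.
- Secondary Objectives still include a between-arm comparison: "To compare specific and generic quality of life at the end of the trial".
- Section 3 says of summaries by arm that "we will present continuous variables as mean, standard deviation (SD), median", followed by IQR and range. Its Univariable analysis paragraph says that between-arm comparisons "will be calculated descriptively and 95% confidence intervals reported, but now no formal" testing. Intervals stay; tests and P-values go.
- Section 4, Continuous secondary outcome, withdraws the linear mixed model: "Again, due to the small sample size given the early termination of the study, this proposed modelling will now not take place". Had it been kept, "The adjusted mean difference with the corresponding 95% CI and P-value will be reported". The only model term named beyond treatment is care trust, as a random effect. The baseline score is not mentioned.
- Section 4, Primary outcome, gives the same reason for dropping adjustment for prognostic baseline factors: "Given the limited sample size, no multivariable model to adjust the treatment effect for" such factors is to be fitted.

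No other part of the SAP plans a baseline-adjusted estimate for these endpoints.

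**The concern.** Read together, these sections leave one between-arm estimate for each continuous secondary endpoint: the raw difference in mean change, with a 95% CI. The SAP does not write this out as a formula, but nothing else is left once the model is removed.

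A change score subtracts the whole of any chance baseline imbalance. When the baseline-to-follow-up correlation is below 1, the follow-up means carry only part of that imbalance. Subtracting all of it over-corrects, and this adds noise. Regression on baseline removes only the part that the data support.

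Small sample size is the only reason given for having no model. It is a fair reason to drop a trust random effect, data-driven covariate selection or causal modelling. It is a poor reason to omit one pre-named covariate, because a smaller trial gains more from each bit of precision. With tests removed, the interval is what tells a reader how precisely the arms were compared.

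**Working it through.** **Inputs from the SAP.** 152 randomised with an assumed 10% loss (Changes to the Statistical Analysis Plan); 1:1 allocation (Study Design); two-sided 95% intervals (section 3). 152 × 0.9 = 136.8, taken as 136, or n = 68 per arm. The 10% is a planning figure, not an observed count.

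**The SAP's own figure.** It gives no precision figure for the secondary endpoints. Its sample size for the primary outcome does reproduce: per arm (0.3×0.7 + 0.2×0.8) × (1.960 + 1.282)² / 0.10² ≈ 388.8, in total 777.5, and 777.5 / 0.9 ≈ 864.

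**Assumed inputs.** The correlation ρ between baseline and follow-up, and k = baseline SD / follow-up SD. Neither is in the SAP, so ranges are shown. Half-widths are in units of the follow-up SD.

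**Formulas, with follow-up SD set to 1.**
- Change-score variance per participant: 1 + k² − 2ρk.
- Baseline-adjusted variance: 1 − ρ².
- Excess: (k − ρ)², which is never negative. At k = 1 the change-score analysis over-corrects an imbalance by (1 − ρ) times its size, and the excess (1 − ρ)² is exactly the variance that this adds. Over-correction and lost precision are therefore one loss, not two.
- Half-width = t × √(2 × variance / n), with 2n − 2 df for change and 2n − 3 df for adjusted. The adjusted variance is multiplied by 1 + 1/(2n − 4) to pay for the covariate.

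**Worked case: ρ = 0.5, k = 1, n = 68.**
- Change: variance 1 + 1 − 1 = 1; 1.978 × √(2/68) = 0.339.
- Adjusted: variance 0.75 × (1 + 1/132) = 0.756; 1.978 × √(2 × 0.756/68) = 0.295.
- Narrowing: 1 − 0.295/0.339 = 13%.
- Width cost of the covariate: √(1 + 1/132) = 1.004, about 0.4%.

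**Equal SDs, 68 per arm.** The last column is 136 × 2/(1 + ρ), the number that a change-score analysis would need for the same precision, ignoring the small covariate cost.

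| ρ | Change half-width | Adjusted half-width | Narrower by | Equivalent N |
|---|---|---|---|---|
| 0.3 | 0.401 | 0.325 | 19.1% | 209 |
| 0.5 | 0.339 | 0.295 | 13.1% | 181 |
| 0.7 | 0.263 | 0.243 | 7.4% | 160 |
| 0.9 | 0.152 | 0.148 | 2.2% | 143 |

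**Sensitivity: narrowing of the interval.**

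| Setting | ρ = 0.3 | 0.5 | 0.7 | 0.9 |
|---|---|---|---|---|
| n = 50 per arm, k = 1 (cost 0.5%) | 18.9% | 12.9% | 7.3% | 2.0% |
| n = 30 per arm, k = 1 (cost 0.9%) | 18.6% | 12.6% | 7.0% | 1.6% |
| n = 68, k = 0.8 | 11.1% | 5.1% | 0.6% | 2.2% |
| n = 68, k = 1.25 | 28.9% | 24.1% | 20.5% | 21.7% |

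**Simulation.** 20,000 trials at n = 68 and k = 1 gave narrowing of 19.0%, 13.1%, 7.5% and 2.2%. Coverage was 94.8–95.2% for change scores and 95.0–95.2% for the adjusted analysis. Both intervals are valid, and the adjusted one is shorter.

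**The case against.** The strongest reply is that nothing here is an error. The unadjusted interval is unbiased and covers as it should, the report is purely descriptive, no decision rule uses the secondary outcomes, and the primary outcome is also left unadjusted, so the SAP is at least consistent. All of that stands, and it limits the point to efficiency. It does not remove it, because the SAP kept the intervals.

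A second reply is that the SAP withdrew a mixed model with trust effects and never said that the sample could not carry one covariate. It is true that the withdrawn model did not name baseline, and that dropping the trust effect is defensible. But sample size is the reason given both for dropping adjustment for baseline factors in the primary analysis and for dropping all modelling here, and nothing replaces it.

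Third, the gain depends on quantities that the SAP does not give and may be only 1–2%. This is correct. The gain is small when ρ is high or when k is close to ρ. Against that, the most that adjustment costs in width in the settings examined is about 0.4% to 0.9%.

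Fourth, the SAP says that the scheduled times for measuring PTS were not kept. If quality-of-life visits drifted too, visit-specific estimates inherit that problem. So do the raw change scores, and adjustment does not repair it.

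Finally, the SAP was signed in May 2023, after the last visit on 31 December 2022, so a further change would be late and must be declared. That is a real but small cost.

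**Conclusion.** The concern holds, as a should-fix point on precision. No baseline-adjusted estimate is planned for VEINES-QOL, EQ-5D or working days, and about 136 participants is no reason to refuse one covariate. The planned intervals are valid but wider than necessary. Under equal SDs and 68 per arm, baseline adjustment would shorten them by 19% to 2% as ρ goes from 0.3 to 0.9. Across SD ratios of 0.8 and 1.25, the gain runs from about 1% to 29%.

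This rests on assumed values of ρ and the SDs, and on the SAP's 10% loss. Fewer participants at a visit hardly alters the percentages, down to 30 per arm. Correct coverage assumes complete or ignorably missing data under either method. For working days, skew or many zeros (an assumption) could make the linear fit poorer and the gain smaller.

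**What to change.** In section 4, Continuous secondary outcome, keep the descriptive status with no P-values and add the following:

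- For VEINES-QOL, the EQ-5D-5L index and the EQ-5D-5L health scale, the between-arm difference at each summarised visit (6 months, 12 months, end of study) is the mean difference from a linear regression of the follow-up value on arm and the baseline value, with its 95% CI. It is shown beside the raw summaries by arm and uses the same allocation of data to visits.
- Baseline is named as the covariate. No other covariate and no trust effect are needed.
- For days working, the same adjustment is used with robust or bootstrap standard errors.

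The cost is SAP wording and one regression per outcome and visit, from data already collected. Participants without a baseline value drop out, as they already do from change scores. The change should be dated and declared as made after data collection ended.
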